Sildenafil for Treatment of Choroidal Ischemia

NCT04356716
April 8, 2020

BACKGROUND

Research Aims & Abstracts

The hypothesis of our study is to determine if there is a benefit afforded by the use of systemic Sildenafil to patients with choroidal and retinal degenerations and dystrophies, such as vitelliform degeneration, dry and reticular AMD as well as patients with hereditary and acquired retinal dystrophies such as retinitis pigmentosa and central serous retinopathy. We theorize that Sildenafil will enhance choroidal perfusion and slow the progression of dry and reticular AMD, as well as vitelliform degeneration, and the associated decrease in vision, as well as reduce the frequency of intraocular injections of anti-VEGF medications. In addition, in patients with acquired retinal conditions such as central serous retinopathy we theorize that sildenafil will enhance resorption of sub-retinal fluid.

We have shown that choroidal insufficiency is one of the causes of macular degeneration. Vitelliform degeneration has been shown to have deposits in the macula that are the same as those in AMD. We have, in a small, off-label series of patients, found that Sildenafil, the generic form of Viagra, can increase choroidal perfusion, and possibly delay or ameliorate AMD, and it should have a similar effect in retinal degenerations and dystrophies or other choroidal degenerative conditions. The drug being offered is Sildenafil similar to the dosage used to treat other diseases such as pulmonary hypertension. The only contraindication that we are aware of is that it cannot be used on patients taking nitrates for heart disease.

Study Purpose and Rationale

Age-Related Macular Degeneration (AMD) is a sight-threatening visual disturbance that affects the macula in older ages. It is irreversible if the pigment epithelium is lost, but wet AMD can be arrested or delayed with the use of intraocular injections of 3 compounds at this time:

1. Avastin: an anti-VEGF (Vascular Endothelial Growth Factor) drug used in ophthalmic off-label use for AM, manufactured by Genentech
2. Lucentis: an Anti-VEGF drug with FDA approval also by Genentech.
3. Eyela: a VEGF trap drug developed by Regeneron.

All three drugs are injected into the eye in minute doses of usually 0.1 mL. These are usually injected at 4 to 6 week intervals and treatment may be extended for several years. Different

We plan to study the results for Sildenafil 20 - 40 mg orally two times a day (a dosage used in treating pulmonary hypertension) in treating vitelliform degeneration or dry AMD, including patients who have had wet AMD in the fellow eye. A small cohort of patients who have a form of dry AMD termed Reticular AMD will also be studied. This form of AMD has small drusen that present as "pox-like" finely scattered drusen that can progress to AMD. Patients with Reticular AMD offer the advantage of small lipid volume and thus are a potentially easier group to quantify resolution using a PDE-5 and PDE-6 inhibitor such as Sildenafil. In addition, we will include other degenerative diseases of the choroid and retina as well as hereditary and acquired retinal

dystrophies, such as central serous retinopathy and retinitis pigmentosa, that may benefit from increased choroidal blood flow.

Study Design

Patients will be enrolled to receive Sildenafil as part of the study. We will also review records of patients who are receiving Sildenafil as part of their standard of care. The study will enroll up to 25 patients with dry AMD, reticular AMD or a combination of wet and dry AMD as well as other macular, retinal and choroidal degenerations and dystrophies. The visual acuity and ocular coherent tomography (OCT) evaluation will be performed as noted under study procedures. We plan to continue the study until up to 25 patients have completed five years of follow-up. This will include patients who are receiving Sildenafil as part of the study and patients who receive Sildenafil for standard care whose charts will be reviewed.

Criteria of visual acuity and number of Lucentis (or other anti-VEGF drugs) injections will be monitored and compared with well documented studies using Lucentis or Avastin or Eylea. OCT and ultrasound measurement of drusen change will be performed and quantified by size and number of drusen.

Patients referred for diagnosis and treatment of AMD as well as other macular, retinal and choroidal degenerations and dystrophies in the practices of Columbia Ophthalmology doctors will be offered inclusion in the study if they have drusen and normal vision in at least one eye. In the course of the study, measurements of vision and Optical Coherence Tomography (OCT). Fundus photography will also be performed at initial exam and if changes are noted on OCT or clinical exam. Visual acuity will be measured.

Systemic Sildenafil will be prescribed for twice a day use. Initial Sildenafil dosage will be weight dependent. Patients will start at 40 mg daily (20 mg in the morning, 20 mg in the evening) or 60 mg daily (40 mg in the morning and 20 mg in the evening). The patient will be followed monthly or bi-monthly as is usual. Sildenafil dosage may be increased to up to 80mg daily (20-40mg in the morning and 20-40mg in the evening) based on the response to lower doses. If the subject has not had improvement after initial treatment, their dose may be increased, at the discretion of the study physician.

Visual acuity along with OCT will be performed at each visit. If available, ultrasound perfusion measurements will be performed within approximately 6 months of starting medication

and approximately 12 months after starting medication. Patients will be treated with Sildenafil only if they choose to enroll in the study.

Patients with AMD will continue to take sildenafil until otherwise directed. Patients with retinal dystrophies and degenerations will take sildenafil until otherwise directed. Patients with central serous retinopathy and other dystrophies with fluid-filled structures will stop one month after OCT testing shows a resorption of fluid from ocular structures. If the fluid-filled structures return, we may restart sildenafil treatment after observing these structures on OCT.

STATISTICAL PROCEDURES

Statistical evaluation will be provided for data using a standard T-test. Patients will be asked to participate for a period of up to 5 years. Results are deterministic, either drusen will improve or they will not. Secondly, the period between injections for wet AMD will be extended or not, compared to the standard treatment protocol. Improvement or maintenance from baseline of visual acuity, contrast sensitivity and OCT and fundus appearance are the end points.

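### In central serous and other fluid-filled disease the hypothesis is fluid resorption, but the only end-point rule accepts unchanged fluid, and response-dependent treatment blurs any late reading

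*Combined protocol and SAP*

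**What the plan says.** The hypothesis is in Research Aims & Abstracts: "in patients with acquired retinal conditions such as central serous retinopathy we theorize that sildenafil will enhance resorption of sub-retinal fluid".

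The end points are in Statistical Procedures, in one sentence for every disease enrolled: "Improvement or maintenance from baseline of visual acuity, contrast sensitivity and OCT and fundus appearance are the end points". The same section adds "Results are deterministic, either drusen will improve or they will not" and a statement on the interval between injections for wet AMD. It names a t-test without saying which variable, groups or time point it applies to.

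The only OCT quantification, in Study Design, is for drusen: "OCT and ultrasound measurement of drusen change will be performed and quantified by size and number of drusen". The external comparison in that section covers visual acuity and injection counts.

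Study Design also sets treatment duration. Patients with central serous retinopathy or other fluid-filled dystrophies "will stop one month after OCT testing shows a resorption of fluid from ocular structures". It continues: "If the fluid-filled structures return, we may restart sildenafil treatment after observing these structures on OCT". For all patients: "If the subject has not had improvement after initial treatment, their dose may be increased, at the discretion of the study physician". OCT is done at every monthly or bi-monthly visit, participation lasts up to 5 years, and up to 25 patients are included across all diseases. The number with fluid-filled disease is not stated.

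**The concern.** Counting a stable eye as a good result is reasonable where the aim is to slow progression, as in dry AMD. It does not suit a disease in which the abnormality is present at baseline and the hypothesis is that it goes away. There, a stable OCT means the fluid persisted and the hypothesis failed in that eye, yet the rule accepts it.

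The second difficulty is timing. Being on drug, off drug or on a higher dose depends on what the OCT has already shown. With up to 5 years of participation and no assessment time fixed, a late comparison with baseline has no clear meaning in terms of treatment.

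At stake is whether the report on this group answers its own question. The OCT end point could be reported as met although no eye cleared. The informative data (when fluid first cleared, and whether it came back after stopping) would be collected without being an outcome.

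**Working it through.** The plan gives no error rate, power, effect size or event rate, and 25 is a cap, so there is no figure to reproduce. The check is mainly a reading of the text. Every rate and subgroup size below is an assumption.

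**1. Hypothesis against end point, for an eye with fluid at baseline**

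| OCT course | Resorption hypothesis | OCT end point as written |
|---|---|---|
| Fluid cleared | supported | met |
| Fluid reduced, not cleared | undefined | met |
| Fluid unchanged | not supported | met |
| Fluid increased | not supported | not met |

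The third row is the fault. No other sentence repairs it: the remaining outcome statements concern drusen, acuity and injections.

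**2. Size of the mismatch.** Leaving out partly reduced fluid,

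P(OCT end point met) = P(cleared) + P(unchanged).

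- Cleared 0%, unchanged 30% to 50%: end point met in 30% to 50%.
- Cleared 40%, unchanged 30% to 50%: end point met in 70% to 90%.

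The excess over the clearing rate equals the unchanged share, here 30 to 50 points. Partly reduced eyes would add to it if resorption means complete clearing.

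**3. What a late OCT would describe.** The stop and restart rules were simulated for a drug with no effect: monthly clearing 3% or 8%, monthly recurrence 0% to 2%, restart at every recurrence, 60 months.

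- At month 60, 56% to 99% of patients were off drug.
- All off-drug patients were fluid-free, against about 3% to 8% of on-drug patients.

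The drug was inert, so that split comes entirely from the stopping rule. It follows from the set-up and shows only that late status by exposure carries no information on effect.

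**4. Is first clearing affected?** Stopping comes after clearing is seen, so it should not be. Expected clearing by 12 months is 1 − (1 − h)^12:

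- h = 0.03: 1 − 0.97^12 = 0.306; simulated 0.306 to 0.307.
- h = 0.08: 1 − 0.92^12 = 0.632; simulated 0.632 to 0.635.

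First-course clearing is therefore usable.

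**5. What a small subgroup can show.** Exact 95% intervals: 0/5 cleared, 0% to 52%; 2/5, 5% to 85%; 5/10, 19% to 81%.

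Power of an exact one-sided test at 0.025 or less, for a 30-point gain over a reference clearing rate of 20% to 50%:

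| Patients | Power |
|---|---|
| 5 | 8% to 19% (no rejection rule exists at a 50% reference) |
| 8 | 17% to 36% |
| 10 | about 38% |
| 25 | 81% to 89% |

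The last row would need all 25 patients to have fluid-filled disease, and the plan supplies no reference rate.

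**The case against.** The best defence is that the end-point sentence covers several diseases: stability suits the slowing of progression, and improvement may be the limb meant for fluid. On that reading the fault is ambiguity rather than a decision to credit persistent fluid. This stands in part. Nothing suggests that the sponsor intends to call persistent fluid a success, but the text exempts no disease, so a literal analyst would have to accept it. The sentence also has no rule for combining acuity, contrast sensitivity, OCT and fundus appearance, so unchanged fluid meets the OCT end point only and need not make the patient a success overall.

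Four stronger readings are tempting, and the documents do not support them.

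- A reader might infer that follow-up compares off-drug responders with on-drug non-responders. No such comparison is planned. The references named are baseline, published anti-VEGF studies and the standard injection protocol. Because restart is optional, an on-drug group would also contain relapsed responders.
- A reader might infer that the fluid question cannot be answered at all. OCT at every visit records first clearing before the stopping rule acts.
- A reader might infer a stated inflation of a pooled success rate. The plan defines no pooled rate and gives no patient counts.
- A reader might infer that the plan expects fluid to return. The restart sentence is conditional.

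A further objection is that the larger obstacle to showing *enhanced* resorption is the lack of any untreated or external comparator for fluid. That is correct. A better end point does not remove it, so the claim has to be limited as well.

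**Conclusion.** The point holds in this form: the end point as written does not measure the resorption hypothesis, and the plan sets no assessment time that avoids the mixing caused by response-dependent stopping, restart and dose increase. The first part rests on the text alone. The second is a risk to any late change-from-baseline analysis, not a fault in an analysis that has been specified.

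The size depends on the share of eyes with unchanged fluid, which the documents do not give; 30 to 50 points is an illustration. The defect affects one of several disease groups, of unstated and probably small size, and can be repaired from OCTs already planned. Even after repair, the study can describe clearing during treatment but cannot show that sildenafil enhanced it. The change should be made before analysis.

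**What to change.** In Statistical Procedures, for patients with central serous or other fluid-filled disease, replace the shared OCT criterion with the following, reported apart from AMD:

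- **End point:** resorption of fluid on OCT in the first treatment course, given as time from first dose to first fluid-free OCT and as the proportion fluid-free by one fixed visit, named in advance. Persistent fluid counts as failure.
- **Definition:** state what fluid-free means, and whether the resorption that triggers stopping is the same thing. The plan does not say whether the trigger is complete or partial clearing.
- **Separate outcomes:** recurrence after stopping, and resorption after restart.
- **Dose:** report how many patients had a dose increase during the first course, and when.
- **Analysis and wording:** give exact intervals for proportions and a time-to-event summary in place of the unspecified t-test, noting that clearing is dated only to the monthly or bi-monthly visit. Describe the result as *resorption observed on treatment*, not as enhanced resorption.
- **Who belongs to the group:** Study Design counts central serous retinopathy among the acquired retinal dystrophies, then gives it a different treatment-duration rule from dystrophies in general. These passages must be reconciled so that the analysis group is unambiguous.

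The cost is protocol and SAP wording plus reading the scheduled OCTs for fluid. Patients included by chart review may lack an OCT at the fixed visit, and their number should be reported. The downside is a narrower, descriptive claim for this group. No dosing or stopping rule changes.

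### Maintenance from baseline is a success end point, but the only analysis named is an unspecified t-test, with no margin, primary measure, eye rule or analysis time tied to it

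*Combined protocol and SAP*

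**What the plan says.** The section Statistical Procedures is a single paragraph.

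- **Method:** "Statistical evaluation will be provided for data using a standard T-test". It does not say whether the test is one-sample, paired or two-sample, or which variable, eye or visit it uses.
- **End points:** "Improvement or maintenance from baseline of visual acuity, contrast sensitivity and OCT and fundus appearance are the end points". None is primary, and nothing separates maintained from worse.
- **Drusen:** "Results are deterministic, either drusen will improve or they will not". No cut-off is given for what counts as improvement.
- **Injections:** the paragraph adds "Secondly, the period between injections for wet AMD will be extended or not, compared to the standard treatment protocol". The reference protocol has no numeric value.

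Study Design adds the following.

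- Acuity and injection number are to be compared with published anti-VEGF studies, which are neither named nor given values.
- Patients "will be offered inclusion in the study if they have drusen and normal vision in at least one eye". No study eye is designated.
- "The patient will be followed monthly or bi-monthly as is usual", and "Visual acuity along with OCT will be performed at each visit".
- The study runs until up to 25 patients have five years of follow-up. They include patients given sildenafil in the study and patients whose standard-care charts are reviewed.
- "Fundus photography will also be performed at initial exam and if changes are noted on OCT or clinical exam".

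**The concern.** Improvement and maintenance call for different evidence. A t-test of zero change can support improvement if the mean gain is significant. It cannot support maintenance, because a non-significant result is also what a small study gives when a real loss is too small for it to detect. To show maintenance, the data must rule out a loss of a stated size, and the plan states none.

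Maintenance is likely to be the main claim. Study Purpose and Rationale makes preserving sight the final aim, and an eye that enters with normal vision has little room to gain acuity.

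Other choices are left open as well: which of four measures, which eye, which of many visits, and which injection reference. If they are made after the data are seen, the end points could be reported as met without evidence that vision was held.

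**Working it through.** **Inputs.** The documents give a maximum of 25 patients (Study Design) and participation of up to five years. They give no significance level, power, SD, effect size or margin, so the figure of 25 cannot be reproduced. Assumed for illustration: two-sided 5% level, one eye per patient, no dropout, and effects in SD of the change from baseline. A size of 10 stands for a single diagnosis or a wet-AMD subset and is also assumed.

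**1. Zero-change test when a real loss exists.** The test statistic follows a noncentral t with n − 1 degrees of freedom and noncentrality d√n, where d is the true mean loss in SD. A non-significant result has probability 1 − power. For n = 25 the critical value is 2.064.

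| True mean loss | d√25 | Power | Non-significant |
|---|---|---|---|
| 0.3 SD | 1.5 | 0.302 | 70% |
| 0.4 SD | 2.0 | 0.484 | 52% |
| 0.5 SD | 2.5 | 0.670 | 33% |

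The 95% interval half-width is 2.064/√25 = 0.413 SD. At n = 10 it is 2.262/√10 = 0.715 SD, and a true 0.5 SD loss is non-significant 71% of the time.

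**2. No primary measure.** Suppose three numeric end points each have a true 0.5 SD loss at n = 25. If they are independent, at least one is not significantly worse with probability 1 − 0.670³ = 0.70, and all three with probability 0.330³ = 0.036. By simulation, at correlation 0.5 these become about 58% and 12%. At correlation 0.8 they are about 48% and roughly one in five. The first figure of each pair matters only if a favourable end point is reported alone.

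**3. Analysis time.** Five years of monthly visits is 5 × 12 = 60 assessments, or 30 if bi-monthly means every two months. The test is attached to none of them.

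**4. Injection reference.** Study Purpose and Rationale describes usual intervals of 4 to 6 weeks, that is 52/4 = 13 to 52/6 = 8.67 a year. It also describes monthly treatment (12 a year) and an observation pattern that gives fewer. As an illustration with assumed data, take 10 injected patients with a mean of 7 a year and SD 3. The standard error is 3/√10 = 0.949 and the 95% interval is 4.9 to 9.1.

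- Against 12: t = (7 − 12)/0.949 = −5.27, p = 0.0005.
- Against 8.67: t = (7 − 8.67)/0.949 = −1.76, p = 0.11.

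With 5 patients and the same SD the p-values are 0.02 and 0.28. With SD 2 and 10 patients the mean is below both references (p = 0.03 against 8.67). The choice of reference can therefore decide the answer, though not for every data set.

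**5. The same data under a margin rule.** Maintenance is claimed if the lower 95% limit lies above −m. With true loss L, the probability is that of a noncentral t with noncentrality (m − L)√n exceeding the critical value. For n = 25 and m = 0.5 SD:

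- L = 0: noncentrality 2.5, probability 67%.
- L = 0.25 SD: noncentrality 1.25, probability 22%.
- L = 0.5 SD: noncentrality 0, probability 2.5%.

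At a true 0.5 SD loss, the risk of a wrong maintenance claim falls from 33% to 2.5%.

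**The case against.** The strongest reply is that the plan never says a non-significant result means maintenance. That stands. A reader might infer such a rule, but the documents do not state one, and every percentage in the zero-change table is conditional on that reading. What remains is that the text permits it and offers no other route to a maintenance claim.

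Three other strong readings are tempting and not supported.

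- **That the plan has no time frame.** Study Design states five years of follow-up, which is a natural final time. The gap is that the test is not tied to it.
- **That stable fundus appearance would rest only on the absence of a photograph.** Repeat photographs are triggered by OCT or clinical examination, and OCT is planned at each visit. The narrower point holds: eyes judged stable have no second photograph to grade against the first.
- **That the t-test will be run on yes/no results.** The paragraph frames drusen and injection interval as yes or no, but it does not say the t-test is applied to them in that form.

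It can also be said that this is a small exploratory study for which descriptive reporting would do. That is fair, but the plan promises a test and names success end points. Finally, the stated goal includes slowing visual loss, and a margin against baseline is a demanding standard when some loss is expected. That stands as a cost of the fix.

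**Conclusion.** The concern holds and should be fixed before outcome data are analysed. Maintenance is a named end point, and a t-test of zero change cannot establish it. If non-significance were taken as maintenance, then at the maximum of 25 patients a true mean loss of 0.3 to 0.5 SD would pass 70% to 33% of the time. These rates rest on an assumed two-sided 5% level and assumed effect sizes, and they illustrate a risk the text leaves open. They do not correct a figure in the plan. The lack of an injection reference value is a second, separate route to a conclusion chosen after the fact. The missing paired photographs limit only the fundus end point.

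**What to change.** Replace the t-test sentence with the following.

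- **(a) Primary end point.** Name one, for example change in visual acuity at five years in one pre-stated eye per patient, or a stated rule for two eyes. Fix it before the analyst sees outcome data, and disclose how much data already exists, since charts are reviewed and the study continues existing work. All other end points are secondary.
- **(b) Numeric measures.** Report the mean paired change with a 95% confidence interval. Claim maintenance only if the interval excludes a loss larger than a margin fixed beforehand in the units of that measure; otherwise report the result as inconclusive. Results by diagnosis are descriptive.
- **(c) Injections.** Report number per patient-year among anti-VEGF-treated patients, with a 95% interval that allows for variation between patients, against one named published value fixed in advance. Patients who stop needing injections stay in with their follow-up time.
- **(d) Yes/no or graded results.** Define the per-patient threshold, and report improved, unchanged and worse separately with exact binomial 95% intervals. Treat fundus appearance as descriptive where no paired photograph exists.
- **(e) Source of patients.** Report study-treated and chart-review patients separately as well as pooled. For chart-review patients, use only measures in their records.

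**Cost.** For study-treated patients, acuity, OCT and injection counts are already planned, so most of this is a change of text. Contrast sensitivity is an end point with no measurement schedule in the text; it needs one or becomes descriptive. The real price is that maintenance is harder to claim. At n = 25 and a 0.5 SD margin the chance is 67% if true change is zero and 22% if the true loss is 0.25 SD. With zero true change, an 80% chance needs a margin of 0.58 SD at n = 25, or 34 patients for a 0.5 SD margin. The study may have to be reported as descriptive. Since every patient receives sildenafil, a successful margin result would show that vision was held, not that the drug held it.

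### Acuity and contrast sensitivity are judged against baseline for up to five years with no concurrent control and no account of the lens, so cataract surgery or lens clouding can be misread as drug effect or its absence (minor)

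*Combined protocol and SAP*

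**What the plan says.** STATISTICAL PROCEDURES defines the vision outcomes in one sentence: "Improvement or maintenance from baseline of visual acuity, contrast sensitivity and OCT and fundus appearance are the end points". It gives no letter threshold, no margin for maintenance, no time point and no rule for choosing the eye. The same paragraph also names drusen change and the interval between injections as outcomes. The only analysis is this: "Statistical evaluation will be provided for data using a standard T-test".

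Follow-up is long. STATISTICAL PROCEDURES says "Patients will be asked to participate for a period of up to 5 years", and Study Design says "We plan to continue the study until up to 25 patients have completed five years of follow-up". Some of these patients are studied by chart review of standard care.

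No concurrent untreated group is planned. Besides baseline, Study Design names an external comparison: acuity and injection counts are to be "compared with well documented studies using Lucentis or Avastin or Eylea".

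Study Purpose and Rationale describes AMD as a "sight-threatening visual disturbance that affects the macula in older ages". It also admits other "dystrophies, such as central serous retinopathy and retinitis pigmentosa, that may benefit from increased choroidal blood flow", and does not describe the ages of those patients. The entry rule in Study Design asks for drusen and for normal vision in one eye or more. The document says nothing about cataract, lens grading, or how to treat readings taken after eye surgery.

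**The concern.** Acuity and contrast sensitivity are measured through the lens as well as by the retina. Over five years in older patients, some lenses will cloud and some may be replaced. In a trial with a concurrent control, such changes would fall on both arms and largely cancel. Here they go straight into the change from baseline, and the t-test cannot tell them from a choroidal effect.

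The error can run either way. An eye limited by its lens at entry and operated on later may read better than baseline, which the plan would call improvement. An eye whose lens clouds enough to fall below baseline would be called a failure to maintain. Contrast sensitivity is exposed in the same way. It is also one of the two benefits reported in the four-patient off-label series in Study Purpose and Rationale, so a lens-related gain there could look like the effect the sponsor hopes to see.

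**Working it through.** The plan gives no surgery rate, letter gain, natural decline or standard deviation, so there is no figure of its own to reproduce. The only input from the documents is the ceiling of 25 patients. Everything else below is assumed, with one eye counted per patient.

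**1. How many operations would hide a decline?** Let k of 25 patients be operated on and gain g letters, and let the other 25 − k lose d letters. The mean change is [k·g − (25 − k)·d] / 25. It reaches zero at k = 25d / (g + d).

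With g = 8:
- d = 1: 25/9 = 2.8, so 3 patients. Check: (3×8 − 22×1)/25 = +0.08, against (2×8 − 23×1)/25 = −0.28 with two.
- d = 3: 75/11 = 6.8, so 7 patients. Check: (7×8 − 18×3)/25 = +0.08.
- d = 5: 125/13 = 9.6, so 10 patients. Check: (10×8 − 15×5)/25 = +0.20.

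The same formula over a wider range of gains, rounded up to whole patients:

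| Assumed gain g | d = 1 | d = 3 | d = 5 |
|---|---|---|---|
| 5 letters | 5 | 10 | 13 |
| 8 letters | 3 | 7 | 10 |
| 15 letters | 2 | 5 | 7 |

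The answer runs from 2 to 13 patients, so no single count can be stated as the effect.

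**2. How likely is any operation at all?** If each patient has probability p of surgery in a study eye within five years, the chance of at least one among 25 is 1 − (1 − p)^25. That is 72% at p = 5%, 93% at 10%, and over 99% at 20% or 30%.

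**3. Effect on the test when sildenafil does nothing.** The mean is biased upward by p × g. A simulated two-sided 5% one-sample t-test on 25 changes from baseline (40,000 runs per setting) should show a significant improvement 2.5% of the time. With surgery it shows:

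| p | g | Bias (letters) | Significant improvement, SD 10 | SD 8 |
|---|---|---|---|---|
| 5% | 5 | 0.25 | 3.2% | 3.4% |
| 10% | 10 | 1.0 | 6.3% | 7.7% |
| 20% | 10 | 2.0 | 13.8% | 18.2% |
| 30% | 15 | 4.5 | 42% | 53% |

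**4. The opposite direction.** If 10% to 40% of patients lose 5 to 10 letters through lens clouding (SD 10), the mean is biased downward by 0.10×5 = 0.5 to 0.40×10 = 4 letters. A significant worsening then appears in 4% to 41% of runs, against the same nominal 2.5%.

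Steps 1 and 3 let any of the 25 gain from surgery. The entry rule and the mixed diagnoses make that generous, so the upper rows should be read as outer limits.

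**The case against.** Several objections have force.

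- **Entry vision.** One eye must have normal vision at entry. If that eye later develops cataract and is operated on, surgery mainly returns it towards baseline and leaves little room for a gain above it. This stands: the upward error belongs mainly to eyes the rule does not cover. It does not remove the point, because the plan does not say which eye is analysed and the rule cannot prevent later clouding.
- **Population.** Older age fits the AMD patients. It cannot be assumed for those with retinitis pigmentosa or central serous retinopathy. This stands.
- **End-point wording.** Maintenance counts as success and no margin is given. A reader might infer that any clouding is scored as failure and any gain as success. The text supports only a narrower statement: clouding matters when measured vision falls below baseline, and surgery matters when it rises above.
- **External comparison.** How the published anti-VEGF studies handled the lens cannot be seen from the protocol. Dropping post-surgery readings here alone could make the two sides less alike. This is a good reason to report both versions.
- **Stopping at surgery.** Used alone, this leaves clouding in the analysis and keeps the readings just before surgery, when the lens may be at its worst. This stands, and the fix allows for it.
- **Unseen text.** Study Design points to study procedures, and no section of that name is in the document as available. A lens examination might be listed there. Even so, STATISTICAL PROCEDURES has no rule for using it.
- **Priority.** The undefined acuity end point and the lack of a concurrent control are the larger weaknesses, and lens change is one consequence of them. That is why the point is rated minor.

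**Conclusion.** The concern holds in a limited form. The direction follows from the plan's own terms: change from baseline, up to five years, no concurrent control, and no rule for lens change or surgery. It applies to acuity and contrast sensitivity only, mainly in the AMD patients, and for upward error mainly in eyes not required to have normal vision at entry.

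The size is not established. A reader might infer that three cataract operations would erase the decline in this trial. That holds only at an assumed 8-letter gain and an assumed 1-letter decline, and the documents support neither figure. Nor do the documents support extending the concern to every outcome: drusen, OCT and injection-interval results are not at issue here. Severity: minor.

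**What to change.** 1. At baseline and follow-up, record lens status for each eye (phakic or pseudophakic), any visually significant opacity noted at the routine examination, and the date of any cataract surgery. Extract the same items for the chart-review patients.
2. State in STATISTICAL PROCEDURES that acuity and contrast readings after cataract surgery do not count as improvement from the original baseline. Show them separately against a new post-surgery baseline.
3. Report acuity and contrast results with and without post-surgery readings, and by lens status, so that clouding in unoperated eyes is also visible.
4. Keep drusen and OCT measures at all visits.

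The cost is a few fields per visit, some chart extraction and a short addition to the analysis text. Some late acuity readings leave the main analysis, and those just before surgery may understate retinal function. Reporting both versions lets the reader see how much depends on that choice. Lens status not recorded during follow-up may be impossible to recover later, so the fields should be added early.
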